Comparative study of retention of mandibular denture bases three- dimensional (3D) printing technique and metal-reinforced acrylic resin

21/7/2022

Abstract

Objective: retention evaluation of mandibular complete denture fabricated by different method

Methods: This in-vivo study was conducted over mandibular complete denture for completely edentulous patients. This study consisted of 2 groups according to method of fabrication of mandibular complete denture: Group I: mandibular complete denture fabricated by 3D printing technique, Group II: mandibular complete denture with metal reinforced fabricated by conventional technique. Retention were evaluated for both groups

Results:

Conclusion:

Keywords: complete denture, metal reinforced denture, retention, Digital, 3D printing

Introduction:

Edentulism has been a serious public health problem in industrialized countries due to population aging and in developing countries due to poor oral care. The life quality and nutrition intake are impacted for edentulous patients due to edentulism. Despite an anticipated decrease in the age-specific rates of edentulism, the demand for complete dentures will continuously increase in the next decades ⁽¹⁾. Edentulism is even classified as a physical handicap by the World Health Organization ⁽²⁾.

Retention plays a vital role in the success of the complete denture, and therefore every stage of denture construction should be given due importance. Effective retention is attained by the close mucosal contact of the denture base. Polymethyl methacrylate (PMMA) is the material of choice for the fabrication of the majority of dentures. During the polymerization process, dimensional shrinkage of the resin occurs. Shrinkage, which is caused by the differences in the densities of the monomer and the polymer, results in a lifting of the denture base away from the posterior palate as a result of polymerization ⁽³⁾.

Alternative materials and techniques are available to overcome the shortcomings of heat cured PMMA, including metal alloys and digital technique. Metal alloys, offer superior mechanical and physical properties in comparison with PMMA. They are stronger, with higher fatigue and fracture strengths. In addition, they can be cast in thin sections without compromising their rigidity or fracture resistance. This property, in addition to their high thermal conductivity, provides patients with a natural “feel” to the prosthesis ⁽⁴⁾.

Metallic denture bases are also biocompatible, dimensionally stable with high surface polish which facilitates hygiene maintenance. They are particularly useful

in situations with high risk of fracture that require strengthening of the denture base, as in cases with bruxism or in single maxillary dentures ⁽⁵⁾.

CAD- CAM technology has been widely used in the field of prosthodontics. Construction of complete denture using CAD- CAM is characterized by ease of fabrication with reduced laboratory procedures. It also leads to higher dimensional accuracy and standardized fabrication ⁽⁶⁾.

Digital design ensures consistent thickness of denture bases which can be adjusted and kept minimal. In addition, the presence of digital data enables future fabrication of dentures in case of lost ones ⁽⁷⁾.

Al helal in 2017 stated that the retention of milled dentures from pre-polymerized poly-methyl methacrylate is better than that of conventional heat polymerized acrylic resin due to less polymerization shrinkage with subsequent superior adaptation. ⁽⁸⁾

Soygun et al in 2013 compared the mechanical properties of polyamide with the conventional PMMA and fiber reinforced PMMA denture base materials; it was revealed that the polyamide denture base material had the highest transverse strength, without any fracture. It was also observed that the values of maximum impact strength were the highest for polyamide (9)

Retention measured by Strain gauge which is a sensor device which is used to convert force, pressure and tension (mechanical strain) in to change in electric resistance (voltage output) that can be measured, it can be used in in-vivo and in-vitro studies⁽¹⁰⁾

Materials and Methods:

Study design:

The National Research Centre's Medical Research Ethics Committee accepted the research protocol on 21/07/2022 (no. of approval: 8887082022).

Completely edentulous patients were selected from the outpatient clinic of the Medical Excellence Centre of the National Research Centre, Cairo, Egypt and College of Oral and Dental surgery, Misr University for Science and technology

according to the following inclusion criteria: patients aged from 45-75 years and had been completely edentulous for a minimum period of 1-year, normal maxillary-mandibular relationship, healthy mucosa, and normal salivary flow. While the exclusion criteria were: smoker patients or patients having hard or soft tissue pathology, severe ridge undercut, and patients who had received radiation to the head and neck region.

This study divided into 2 groups according to type of denture received by the patients:

Group I: Patients received maxillary and mandibular rapid prototype complete denture

- Retention was measured at time of insertion and after 3 week and after 6 week using the retention force gauge device

Group II: Patients received mandibular complete denture constructed from polyamide reinforced with metal frame work and maxillary dentures constructed from conventional Poly-Methyl Methacrylate

- Retention was measured at time of insertion and after 3 week and after 6 week using the retention force gauge device

Sample Size Calculation:

A total sample size of 12 will be sufficient with the power of 80% and 5% significance level. This number will be increased to 20 (10 in each of the two groups) to compensate for follow-up losses. The sample size was determined through the application of the G Power program.

Construction of the 3D model:

For rapid prototype complete denture base, Preliminary impressions was made using irreversible Hydrocolloid Alginate (Cavex Holland BV) then definitive impression and recorded horizontal relationship were done in one visit and sent to a digital laboratory for scanning and 3D printing of the CDs.

The master casts were digitalized using and extraoral 3D scanner * , at which the cast holder used to fix the cast in place,

The digital image (STL file) were imported to Exocad* digital design software to oriented the cast according to proposed insertion and removal pathway and to draw extension of denture base at the depth of vestibules and make design of denture base.

Printing step: the designed denture base were export as STL file and sent to 3D printer software, the denture base were printed according to Digital Light projection (DLP) technology * using Next Dent Baes Liquid* which is a monomer based on acrylic ester. Then the denture base were finished and polished except area at crest of the ridge.

Bite registration using printed denture base: wax occlusal rim were made on the printed denture base, then inserted in patient mouth to adjust lip support and vertical diminution and for registration jaw relation (centric relation)

Setting artificial teeth were carried on the same way as in conventional complete denture, after try in maxillary and mandibular denture, the artificial teeth attached to digital denture base by self cured acrylic resin.

Finally the finished denture was inserted in patient mouth to checking retention and stability and occlusion

* [contact] [contact], [name]

* Exocad GmbH [name]

* Digital light projection (DLP): Mogassam Dentcase printer, Delaware, USA

* Next Dent base liquid: by 3D systems, Soesterberg, Netherlands

Construction of metal reinforced complete denture:

Maxillary and mandibular preliminary impressions were made for each patient using irreversible hydrocolloid impression material (alginate) in stock tray then special trays were constructed for final impression registration.

Centric relation at the proper vertical dimension of occlusion was recorded using wax wafer registration, and then Trial dentures were tried in the patient's mouth for appropriate vertical and horizontal maxilla-mandibular relation

Finally, duplication of the master cast using silicon material was done to obtain a refractory cast for the construction of the metal framework

Metal framework: Two rows of mesh wax pattern were adapted on the refractory cast, followed by spruing, investing, burning out and casting of the metal framework.

The metal framework was returned in to the master cast and checked for adaptation. Sealing of the mandibular trial denture base to the master cast, waxing up and attaching the sprue formers was done to make the channels for injection of polyamide into mold, The cartridge was placed in a cartridge carrier which was then placed in electric cartridge furnace* used for softening of thermoplastic denture base material. The cartridge was placed on the inlet of the flask and was compressed in mechanical compressor.

Finally Denture insertion was made checking extension, retention, stability and occlusion

* Thermopress Flask, Bredent, GmbH, Senden/ Witzighausen, Germany

Retentive force Measurements

The measuring device used to measure retention is Digital force gauge *(is an advanced type of force meter device used to Measure Tension or Compression force.

After determining the geometric center for mandibular denture, then mark a point on the plaster base.

Three “V” shaped grooves were created on the polished surface of the lower denture. (Two grooves were created at the retromolar pad area just distal to the second molar of both sides. The other one was made on the lingual flange at the midline region below the central incisors)

A wrought wire of 1 mm in diameter was then bent at its center and adjusted so as not to encroach on the tongue space and to run 2 cm above the occlusal plane from the retromolar pad groove of one side to the retromolar pad groove of the other side.

* Digital Force Gauge EXTECH 475044.

Then free ends of the three wires were then fixed to the polished surface of the lower denture by self-cured acrylic resin.

Retention of mandibular dentures was assessed as follows:

After denture insertion, The metallic probe of the digital force-meter was then attached to the c-shaped metal hook created at the geometric center of the mandibular dentures and a vertical pulling force was applied to measure denture retention. Retention strength was measured in newtons.

Statistical analysis:

All data were presented as mean & standard deviation. Data were presented 1 table & 1 graph. Statistical analysis was performed with SPSS 16 ® (Statistical Package for Scientific Studies), Graph pad prism & windows excel

Exploration of the given data was performed using Shapiro-Wilk test and Kolmogorov-Smirnov test for normality which revealed that the significant level (P-value) was insignificant as P-value > 0.05 which indicated that all data originated from normal distribution (parametric data) resembling normal Bell curve.

Accordingly, comparison between different groups was performed by using Independent t-test, while comparison between different intervals was performed by using One Way ANOVA test followed by Tukey's Post Hoc test for multiple comparisons.

Effect of time (table 1 and figure 1):

In group I, there was a significant difference between all intervals as $P<0.05$, at delivery was significantly the lowest retention (10.58 ± 0.31), while there was

insignificant difference between after 3 months (11.92 ± 0.56) and after 6 months (12.17 ± 0.49) with 15.9% percent of increase in retention for 6 months.

In group II, there was a significant difference between all intervals as $P<0.05$, at delivery was significantly the lowest retention (16.54 ± 0.52), then after 3 months (18.49 ± 0.58), while after 6 months (19.87 ± 0.59) was significantly the highest with 20.00% percent of increase in retention for 6 months.

Effect of different construction techniques (table 2 and figure 2):

Comparison between group I & II revealed that group II was significantly higher than group I at all intervals as $P <0.05$

Table (1): Mean and standard deviation of retention in both groups and comparison between different intervals with percent of change in each group:

	Follow up	M	SD	% change	P value
Group I (3D printed denture)	At delivery	10.58 ^a	0.31	15.90%	<0.0001*
	After 3 weeks	11.92 ^b	0.56		
	After 6 weeks	12.17 ^b	0.49		
Group II (metal reinforced denture)	At delivery	16.54 ^a	0.52	20.00%	<0.0001*
	After 3 weeks	18.49 ^b	0.58		
	After 6 weeks	19.87 ^c	0.59		

M: mean

SD: standard deviation

*Significant difference at $P <0.05$

Means with different superscript letters were significantly different as $P <0.05$

Means with the same superscript letters were insignificantly different as $P >0.05$

[figure not shown]

Figure (1): line chart representing retention changes of both groups during different intervals.

Table (2): Comparison between group I & II regarding retention at different intervals using Independent t-test:

Interval	N	Group I		Group II		Independent t-test			
						P value	MD \pm SEM	95% CI	
		M	SD	M	SD			L	U
At time delivery	7	10.58	0.31	16.54	0.52	0.0001 *	5.9 \pm 0.2	5.4	6.4
After 3 weeks	7	11.92	0.56	18.49	0.58	0.0001 *	6.6 \pm 0.3	5.9	7.2
After 6 weeks	7	13.24	0.49	19.87	0.5	0.0001 *	6.63 \pm 0.3	6.05	7.21

M: mean SD: standard deviation *Significant difference at $P < 0.05$

Difference between means ($B - A$) \pm standard error of mean

CI: confidence intervals at 95% (U: upper / L: lower)

[figure not shown]

Figure (2): Bar chart representing retention in both groups.

REFERENCES

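### No rule is described for who received which denture, yet the unadjusted difference between groups is headed as an effect of construction technique

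*Combined protocol and SAP*

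**What the plan says.** The groups are defined twice. The Abstract (Methods) says "This study consisted of 2 groups according to method of fabrication of mandibular complete denture". Study design says "This study divided into 2 groups according to type of denture received by the patients". Neither place, nor any other, gives an allocation method.

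The two arms are described in Study design as follows:
- "Group I: Patients received maxillary and mandibular rapid prototype complete denture"
- "Group II: Patients received mandibular complete denture constructed from polyamide reinforced with metal frame work and maxillary dentures constructed from conventional Poly-Methyl Methacrylate"

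Recruitment is from two institutions: "National Research Centre, Cairo, Egypt and College of Oral and Dental surgery, Misr University for Science and technology". One set of eligibility criteria applies to all patients. Sample Size Calculation plans 10 patients in each group.

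Statistical analysis compares the groups by an independent t-test, with no term for site or for any patient characteristic. The result stands under the heading *Effect of different construction techniques* and reads "Comparison between group I & II revealed that group II was significantly higher than group I at all intervals".

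**The concern.** A two-sample t-test supports a statement about cause only if the way patients reached the groups is unrelated to their prognosis for retention. Here the reader is not told how they reached the groups. If the choice of denture was left to the clinician, the patient or the site, group membership could carry differences in ridge form, age, time since tooth loss, site or operator. The Introduction shows one route by which this could happen: it describes metal bases as especially useful where the risk of fracture is high, for example in bruxism. That is a possible route, not evidence that it was taken.

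This is the study's only between-group comparison, so what is at stake is whether its difference can be read causally and whether its size can be trusted.

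**Working it through.** **1. Search for an allocation rule.** The Abstract, Study design, Sample Size Calculation, the two construction sections, the retention measurement section and Statistical analysis contain no randomisation, sequence, concealment, matching or other assignment rule. There is no table of baseline characteristics and no count of patients by site and group.

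**2. Reproduce Table 2.** Inputs are the Table 2 means and SDs, with its N of 7 taken as per group (df = 12, t = 2.179). SE = sqrt((SD1² + SD2²)/7), and half-width = 2.179 × SE.

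| Time | Difference (N) | SE | Recomputed 95% CI | Table 2 |
|---|---|---|---|---|
| Delivery | 16.54 − 10.58 = 5.96 | sqrt((0.31² + 0.52²)/7) = 0.229 | 5.46 to 6.46 | 5.4 to 6.4 |
| 3 weeks | 18.49 − 11.92 = 6.57 | sqrt((0.56² + 0.58²)/7) = 0.305 | 5.91 to 7.23 | 5.9 to 7.2 |
| 6 weeks | 19.87 − 13.24 = 6.63 | sqrt((0.49² + 0.5²)/7) = 0.265 | 6.05 to 7.21 | 6.05 to 7.21 |

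The intervals reproduce; the delivery row does so if the difference is taken as 5.9. The delivery half-width is 2.179 × 0.229 = 0.50 N. (Table 1 gives 12.17, not 13.24, for Group I at 6 weeks. That needs reconciling separately and does not affect this point.)

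**3. What the intervals leave out.** The differences are about 11 to 14 pooled SDs, so chance is not the question. The intervals describe sampling error only. For a factor such as site:

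bias = (difference between groups in the share of patients with the factor) × (effect of the factor on retention).

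The documents give neither term. What can be worked out is the effect needed for the bias to reach a given size at delivery:

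| Difference in share | Effect for bias of 0.50 N | Effect for bias of 5.96 N |
|---|---|---|
| 1 (each group from one site) | 0.50 N | 5.96 N |
| 0.5 | 1.0 N | 11.92 N |
| 0.25 | 2.0 N | 23.84 N |

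Even with complete alignment, removing the gap needs an offset of 5.96/10.58 = 56% of the Group I delivery mean.

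**4. A rough limit from the reported SDs.** This assumes that both sites fed both groups and that the site effect was the same in each. A share q at one site then adds about q(1 − q) × effect² to the within-group variance, so the Group I SD of 0.31 N limits the effect.
- At a 10:90 mix, effect ≤ 0.31/sqrt(0.1 × 0.9) = 1.03 N. Opposite mixes in the two groups give bias ≤ 0.8 × 1.03 = 0.83 N.
- With 7 per group, the most uneven mix is 1 to 6. The sample SD from site alone is then effect/sqrt(7), so effect ≤ 0.31 × sqrt(7) = 0.82 N and bias ≤ (6/7 − 1/7) × 0.82 = 0.59 N.

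So opposite, very uneven mixes could add about 0.6 to 0.8 N, which is 10% to 14% of 5.96 N and more than the 0.50 N half-width. If each group came from a single site, the SDs set no limit. If the site shares were equal, the site bias is zero.

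**5. What random allocation would settle.** The arms differ in mandibular base material, metal framework, fabrication route and maxillary denture. Randomising patients would make the comparison of these two packages fair. It would not separate fabrication technique from the other components, or from a laboratory that goes with one type of denture.

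**The case against.** Silence is not a statement. Naming groups by the denture received is ordinary wording that a randomised study could also use, and equal planned groups of 10 fit assigned arms well. A reader might infer that allocation was non-random, or that whoever chose the denture chose the group. The documents do not support either inference; they support only that no rule is described.

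Eligibility also narrows some of the threats. It requires normal salivary flow, healthy mucosa, a normal jaw relationship and age 45 to 75, and it excludes smokers, severe ridge undercut, tissue pathology and head and neck radiation. This stands, most directly for saliva. It still leaves a 30-year age range, only a 1-year minimum of edentulism, and ridge form limited only at the extreme.

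The causal wording lies mainly in a section heading that parallels the one on time. The sentence beneath it states only a difference, and the abstract's conclusion is blank. That is fair, and it is why rewording the heading goes most of the way.

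Finally, any particular site offset in newtons would be an unsupported assumption, and a large one needs site and denture to be almost fully aligned, which no section suggests. This stands too: the figures above are conditional and do not estimate a bias. None of it supplies the missing allocation rule or site split.

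**Conclusion.** The point holds in this form: the documents describe no rule for assigning dentures, patients come from two institutions with no split by group, and an unadjusted difference is headed as an effect of technique. The difference of about 6 N may include selection or site bias that the Table 2 intervals do not cover, and the documents do not allow its size to be determined. If both sites served both groups with a common site effect, the reported SDs suggest that site alone could explain only a small part of the gap. If site and denture were fully aligned, the data set no limit.

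A reader might go further and conclude that the gap is an artefact. The documents give no ground for that. It would take an offset of about 6 N, and reversal is unlikely. The damage is to attribution and to the precision claimed for the estimate. This should be corrected, with medium confidence, because one sentence documenting random assignment would remove most of it.

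**What to change.** **Patients not yet treated.** Allocate 1:1 by a computer-generated sequence, concealed from those who recruit and stratified by recruiting site, and compare groups as allocated. This costs a list held by someone outside recruitment and a paragraph in Study design; it needs no extra patients.

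**Data already collected.** Results are already reported, so this is the part that applies to them.
- State how each patient's denture was assigned.
- Tabulate site, age and years edentulous by group.
- Unless random assignment can be documented, label the study a non-randomised comparison and replace the causal heading with one that states a difference between groups.

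**In either case.** Describe the contrast as printed upper and lower dentures versus a metal-reinforced polyamide lower with a PMMA upper, not as construction technique alone.

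The downside is a weaker stated claim and a little extra reporting.

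### Does analysing 7 patients per group in Table 2, against 10 per group planned, call for a change to the plan?

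*Combined protocol and SAP*

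**What the plan says.** The Sample Size Calculation section gives a minimum: "A total sample size of 12 will be sufficient with the power of 80% and 5% significance level". It then gives a recruitment target: "This number will be increased to 20 (10 in each of the two groups) to compensate for follow-up losses". No expected loss rate is stated, and the inputs to the calculation are not given beyond "The sample size was determined through the application of the G Power program".

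Table (2) carries a single N column. It shows 7 on every row: "At time delivery 7 10.58", "After 3 weeks 7 11.92" and "After 6 weeks 7 13.24". Table (1), which holds the within-group comparisons over time, has the column headings "Follow up M SD % change P value" and no count.

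No section gives the number enrolled, allocated, fitted or measured, a reason for any loss, or a rule for missing readings.

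**The concern.** The only reason given for going from 12 to 20 is loss during follow-up. The delivery reading is taken at insertion, so later dropout cannot by itself bring that row down to 7. Four explanations stay open:

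- fewer than 20 patients were recruited;
- patients were lost before insertion, during impressions, jaw registration and try-in (in the printed-denture group, for example, "after try in maxillary and mandibular denture, the artificial teeth attached to digital denture base by self cured acrylic resin");
- some readings failed or were excluded;
- only patients with all three visits were analysed, so later dropouts were also removed from the delivery row.

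The last would matter most. Retention is the outcome, and a loose denture is a plausible reason for not returning. A completers-only analysis could then overstate mean retention and the reported rises over time (15.9% and 20.00%). Loss before insertion that differed between the two workflows could make the groups less comparable.

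**Working it through.** **1. Is the 7 per group, and is it real?** Inputs are the means, SDs and 95% limits printed in Table (2). With equal groups of n, the half-width is t(0.975; 2n−2) × √[(SD₁² + SD₂²)/n].

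Delivery, n = 7: √[(0.31² + 0.52²)/7] = 0.229; × 2.179 = 0.499; width 1.00. At n = 10: 0.191 × 2.101 = 0.402; width 0.80.

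| Row | SDs (I, II) | Printed limits (width) | n = 7 | n = 8 | n = 10 |
|---|---|---|---|---|---|
| Delivery | 0.31, 0.52 | 5.4 to 6.4 (1.0) | 1.00 | 0.92 | 0.80 |
| 3 weeks | 0.56, 0.58 | 5.9 to 7.2 (1.3) | 1.33 | 1.22 | 1.07 |
| 6 weeks | 0.49, 0.50 | 6.05 to 7.21 (1.16) | 1.15 | 1.06 | 0.93 |

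Rounding of the printed limits allows true widths of 0.9 to 1.1, 1.2 to 1.4 and 1.15 to 1.17. Ten per group falls outside on every row. Seven per group fits all three, and at 6 weeks it reproduces the limits exactly (6.05 to 7.21). Seven in total (4 + 3) would give widths of 1.60, 2.23 and 1.94, so the 7 is per group.

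One caveat: Table (1) prints 0.59, not 0.5, for the Group II SD at 6 weeks. With 0.59 the 6-week width is 1.26 at n = 7, 1.16 at n = 8 and 1.02 at n = 10. The exact 6-week match at 7 therefore rests on Table (2)'s own SD. Ten is excluded either way. The two tables also differ on the Group I mean at 6 weeks (12.17 against 13.24), which is a separate matter.

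**2. How large is the shortfall against the plan?** 20 − 14 = 6, and 6/20 = 30%. The planned margin is 1 − 12/20 = 40%. Fourteen is above 12.

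**3. Is power lost?** The 12 cannot be reproduced, because no effect size or SD is given. Assume a two-sided two-sample t-test with 6 per group at 80% power. The standardised difference that gives this is about 1.80. At that value power is about 87% with 7 per group and 97% with 10. One-sided, the figures are 1.54, 86% and 95%. Either way 7 per group stays above the stated 80%.

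**4. Could the absent patients overturn the result?** Difference over pooled SD: 5.96/0.428 = 13.9 at delivery, 6.57/0.570 = 11.5 at 3 weeks, 6.63/0.495 = 13.4 at 6 weeks.

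Suppose, as the worst case, that 10 per group were fitted and 3 per group left out. The full difference is (7 × observed difference + 3 × difference among the omitted)/10. It reaches zero only if the omitted patients differ in the opposite direction by:

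- delivery: 7 × 5.96/3 = 13.9 N;
- 3 weeks: 7 × 6.57/3 = 15.3 N;
- 6 weeks: 7 × 6.63/3 = 15.5 N.

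The largest SD in either table is 0.59 N, so a reversal of that size is not credible.

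**The case for a change.** The strongest case for acting is that this document reports results, so the achieved numbers belong in it. A margin for loss does not excuse silence about who was analysed, and the delivery row shows that follow-up loss alone is not the explanation. Supplying the counts would need only existing records.

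Much of that stands. The counts are absent, the 7 is not a misprint, and a reader cannot tell whether the 14 are everyone fitted or a subset. Patient counts by group and visit would be good reporting.

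It falls short of requiring a change. Each route to bias is conditional: on completers-only analysis, on loss related to retention, or on loss that differed by workflow. The document supports none of these over plain under-recruitment, which would involve no selection through dropout. The two analysed groups are equal in size, so unequal loss is not visible. Reanalysis would make sense only if readings beyond 7 per group exist, and nothing indicates that they do.

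**Conclusion.** No change to the plan. A target of 20 and an analysed number of 14 do not contradict each other: the margin was set so that fewer than 20 could be analysed, and 14 exceeds the 12 described as sufficient. The shortfall of 6 (30%) is within the 40% margin implied by going from 12 to 20, although its timing is unexplained. The missing counts are a reporting gap, not an arithmetic error, and filling it would leave every test, interval and conclusion as it is.

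This rests on taking Table (2)'s N as per group, which its intervals support, and on the absence of any sign that more than 7 per group were measured. If further delivery readings did exist, an analyst would ordinarily include everyone measured. The direction of the between-group difference would be safe even then. The size of the rise over time is less protected against selective loss, but no such loss is shown.

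### Repeated visits on the same patients are analysed as independent samples, change is never compared between groups, and the conflicting Group I 6-week mean must be settled before a rerun

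*Combined protocol and SAP*

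**What the plan says.** Under Study design, the same statement is made for each group: "Retention was measured at time of insertion and after 3 week and after 6 week using the retention force gauge device". The three readings therefore come from the same patients.

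The Statistical analysis section names two methods. For groups, "comparison between different groups was performed by using Independent t-test". For time, "comparison between different intervals was performed by using One Way ANOVA test", with Tukey comparisons afterwards. No paired, repeated-measures or mixed-model method, and no group-by-time term, is named anywhere.

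The Effect of time text reports for Group I an "insignificant difference between after 3 months (11.92 ± 0.56) and after 6 months (12.17 ± 0.49"), and for Group II a significant rise at each step, "with 20.00% percent of increase in retention for 6 months". Table 1 is headed as a "comparison between different intervals with percent of change in each group" and prints gains of 15.90% and 20.00%. Table 2 is a "Comparison between group I & II regarding retention at different intervals using Independent t-test"; it tests the level at each visit and not the change.

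The 6-week row differs between the tables. The Group I mean is 12.17 in Table 1 and the text but 13.24 in Table 2. The Group II SD is 0.59 in Table 1 and 0.5 in Table 2.

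**The concern.** A one-way ANOVA leaves the variation between patients in the error term and assumes that readings at different visits are independent. If a patient's readings are positively correlated, the tests of time are conservative, so a statement of no difference is the kind most at risk. The plan makes one such statement, for Group I between 3 and 6 weeks.

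Printing two percent gains side by side invites the reader to compare them, but the plan gives no estimate, interval or test for that comparison. Neither gap can be filled from the printed tables while they disagree on the Group I 6-week mean.

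**Working it through.** **Inputs.** Means (SD) in newtons at delivery, 3 weeks and 6 weeks. Group I: 10.58 (0.31), 11.92 (0.56), and 12.17 or 13.24 (0.49). Group II: 16.54 (0.52), 18.49 (0.58), 19.87 (0.59 in Table 1, 0.5 in Table 2). I take n = 7 per group from the N column of Table 2. The documents give no within-patient correlation (rho), so I show a range.

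**1. Reproducing Table 1.** F = n × variance of the three means / mean of the squared SDs, on 2 and 18 df.

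- Group I with 12.17: 5.117 / 0.2166 = 23.6, p = 9e-6. Tukey p for 3 v 6 weeks is 0.58. The printed letters a/b/b reproduce.
- Group I with 13.24: 12.383 / 0.2166 = 57.2. Tukey p for 3 v 6 weeks is 0.0001, so the letters would be a/b/c.
- Group II: 19.595 / 0.3183 = 61.6, p = 9e-9. The letters a/b/c reproduce.

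**2. Reproducing Table 2 at 6 weeks.** 19.87 − 13.24 = 6.63. With SDs 0.49 and 0.5 the 95% CI is 6.05 to 7.21, exactly as printed. With 12.17 and SD 0.59 it would be 7.70 (7.07 to 8.33). So Table 1 rests on 12.17 and Table 2 on 13.24.

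**3. Calibration of the one-way test.** This used 40,000 simulated data sets per rho (7 patients, 3 visits, equal correlation, no time effect).

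| rho | One-way ANOVA rejects at nominal 5% |
|---|---|
| 0 | 5.1% |
| 0.3 | 2.0% |
| 0.5 | 0.8% |
| 0.7 | 0.2% |

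Repeated-measures ANOVA stays at 4.9% to 5.1%.

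**4. What changes under a repeated-measures analysis.** I used the Table 1 SDs with covariance rho × SDi × SDj and a Greenhouse-Geisser correction. For rho from 0 to 0.9 the overall time effect has p ≤ 0.0002 in Group I and p ≤ 1e-6 in Group II. Five of the six visit contrasts have Tukey p < 0.001, and Bonferroni paired p ≤ 0.014 at rho 0, 0.5 and 0.9.

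The sixth contrast is Group I, 3 v 6 weeks: t = change / (SD of change / √7) on 6 df, with SD of change = √(0.56² + 0.49² − 2 × rho × 0.56 × 0.49).

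| rho | Change 0.25 N (mean 12.17), Bonferroni p |
|---|---|
| 0.5 | 0.77 |
| 0.8 | 0.30 |
| 0.9 | 0.11 |
| 0.94 | 0.043 |

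With 12.17 the result falls below 0.05 only for rho above about 0.88 unadjusted, or about 0.94 with Bonferroni. With 13.24 the change is 1.32 N and the Bonferroni p is 0.010 even at rho 0.

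**5. Percent gains, delivery to 6 weeks.** Group I: 12.17 / 10.58 gives +15.0%, and 13.24 / 10.58 gives +25.1%. The stated 15.9% matches neither. Group II: 19.87 / 16.54 gives +20.1%.

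**6. Difference in gain, Group II minus Group I.** Group II gains 19.87 − 16.54 = 3.33 N. Group I gains 1.59 N (12.17) or 2.66 N (13.24). Welch intervals on change scores, Group II 6-week SD 0.59:

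| Group I 6-week mean | Difference | 95% CI, rho 0 | 95% CI, rho 0.5 |
|---|---|---|---|
| 12.17 | 1.74 N | 0.93 to 2.55 | 1.16 to 2.32 |
| 13.24 | 0.67 N | −0.14 to 1.48 | 0.09 to 1.25 |

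The second row pairs a Table 2 mean with a Table 1 SD. With Table 2's SD of 0.5 its intervals are −0.10 to 1.44 and 0.12 to 1.22, and the reading is the same.

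**The case against.** The strongest reply is that the choice of test alone changes almost nothing. Its error is conservative under positive correlation, so no significant finding is inflated, and with the Table 1 mean the plateau statement gives way only at very high correlation. What moves the conclusions is the conflict between 12.17 and 13.24, which is a reporting fault and would matter equally under a perfect model. That is right, and it is why reconciliation has to come first. It does not make the named test suitable for the design.

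Second, the objective is to compare retention by fabrication method, Table 2 answers that visit by visit, and the text never says that one group gained more. This also stands in part. The comparison of change is an addition and no stated claim rests on it. However, the gains are reported for both groups in one table, and a reader will compare them.

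Third, a matched ANOVA may have been run and described loosely. The printed p < 0.0001 cannot settle that. If so, the wording still needs correcting, and the table conflict and the missing comparison of change remain.

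**Conclusion.** The concern holds, as something that should be fixed but does not overturn the main result. The time comparison as described is wrong for repeated readings on the same patients, and change is not compared between groups. The independent t-tests at each visit do not depend on within-patient correlation, and Group II is higher at every visit whichever 6-week mean is right (6.63 N or 7.70 N at 6 weeks).

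Two readings are unsafe until the 6-week value is settled. One is the Group I plateau from 3 to 6 weeks. The other is the comparison of gains: with 12.17 Group II gains more in percent (20.1% v 15.0%), while with 13.24 Group I gains more in percent (25.1% v 20.1%) but less in newtons (2.66 v 3.33).

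These figures rest on 7 patients per group, the printed SDs and an assumed range of rho. Exact results need the patient-level data.

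**What to change.** 1. **Reconcile to source data first:** the Group I 6-week mean (12.17 or 13.24), the Group II 6-week SD (0.59 or 0.5), the 15.9%, and the visit labels (weeks in the design and tables, months in the results text). Also account for N = 7 in Table 2 against 10 planned per group, and correct the Group I sentence that claims differences between all intervals and then reports none between the last two.

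2. **Replace the one-way ANOVA sentence** with wording such as the following, marked as a post hoc correction because results are already reported:

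   > Retention in newtons was analysed by a mixed repeated-measures ANOVA with group (between patients), visit (within patients) and group-by-visit, with Greenhouse-Geisser correction and patient as the repeated unit. Within each group the three visit contrasts were paired, with Bonferroni adjustment. The between-group difference in change from delivery to the last visit is given in newtons with a 95% CI, from a Welch t-test on patient change scores. Percent change is descriptive.

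   If any patient missed a visit, use a linear mixed model with the same terms and small-sample degrees of freedom.

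3. **Keep the independent t-tests at each visit**, and rerun the 6-week row if its mean or SD changes.

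The cost is a source-data check, a wording change and a rerun on data already collected.
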